12.1.7.1 Virus Serology

Subjects will be tested for hepatitis B surface antigen, anti-hepatitis C virus antibody or hepatitis C antigen (RNA), and human immunodeficiency virus (HIV-1 and HIV-2) antibody during Screening.

12.1.7.2 Pregnancy Screen Testing

~~A~~ Serum pregnancy (**human chorionic gonadotropin**) tests will be conducted for all female participants ~~at~~**during** Screening; a urine pregnancy tests will be conducted for all female participants that are not postmenopausal or surgically sterile at other scheduled time points. Follicle stimulating hormone testing will be conducted during Screening to confirm whether a participant with ≥ 12 months of spontaneous amenorrhea meets the protocol-defined criteria for being postmenopausal (Section 8.1). **A urine pregnancy test will also be performed as part of the early termination assessments for subjects who discontinue the study early.**

If a participant becomes pregnant during the study, the process for reporting the pregnancy and guidance for collection of information related to the pregnancy is outlined in Section 12.3.

Sections also affected by this change: Synopsis

Purpose: *The abbreviated physical examination has been defined to provide clarity and consistency.*

The primary change occurs in Section 12.1.3..

Revised text:

Thereafter, abbreviated physical examinations will include ~~a brief medical history~~ **assessment of general appearance, cardiovascular, respiratory, gastrointestinal, and neurological systems**, followed by a targeted physical examination **as needed**.

Sections also affected by this change: Synopsis

Purpose: *Oxygen saturation has been removed from the list of vital signs to be documented, in alignment with other SAGE-718 protocols, as well as the specification that temperature must be taken orally.*

The primary change occurs in Section 12.1.4..

Revised text:

Vital signs comprise heart rate, respiratory rate, ~~oral~~ temperature ($^{\circ}\text{C}$), **oxygen saturation**, and blood pressure.

Sections also affected by this change: Synopsis

Purpose: [REDACTED]

The primary change occurs in Section 11.2.2, Pharmacodynamic Assessments.

Revised text:

11.2.2 Pharmacodynamic Assessments

[REDACTED]

[REDACTED]

[REDACTED]

[REDACTED]

Sections also affected by this change: Synopsis

Purpose: *Correct typographical errors, punctuation, grammar, abbreviations, and formatting.*
These changes are not listed individually.

4.0 Purpose

The Statistical Analysis Plan (SAP) describes the statistical methods to be used during the reporting and analyses of data collected under Sage Therapeutics Protocol 718-CNP-201: An Open-Label Evaluation of the Safety and Tolerability of SAGE-718 in Participants with Parkinson's Disease Mild Cognitive Impairment 718-CNP-201.

5.0 Scope

This SAP describes the statistical methods to be used during the reporting and analyses of data collected from Sage Therapeutics Protocol 718-CNP-201, titled "An Open-Label Evaluation of the Safety and Tolerability of Sage-718-201 in Participants with Parkinson's Disease Mild Cognitive Impairment".

The Statistical Analysis Plan outlines the following:

- Study Objectives
- Study Design
- Study Endpoints
- The Analysis sets
- Applicable Study Definitions
- Statistical Methods

6.0 Introduction

This is an open-label study evaluating the safety and tolerability of SAGE-718 and its effects on [REDACTED] in participants with PD-MCI. Eligible participants with a confirmed diagnosis of idiopathic PD by 2015 Movement Disorder Society (MDS) criteria at Screening and who meets MDS Task Force Criteria for MCI in PD (excluding the requirement for UK PD Brain Bank diagnostic criteria) will receive a 3.0 mg dose of SAGE-718 daily for 14 days (Part A) or 28 days (Part B).

This SAP should be read in conjunction with the study protocol and case report form (CRF). This version of the plan has been developed using the protocol version 5 dated 28-Apr-2021 and CRF dated 16-Oct-2020 for Part A and CRF dated 09-Aug-2021 for Part B.

Changes to the protocol will require an SAP amendment ONLY if the changes are to a principal feature of the protocol.

Final approval of the SAP by the Sponsor and PRA statistician will occur prior to database lock. Any changes made to the SAP after the clinical database lock, along with the justification for the changes, will be described in the CSR.

6.1 Changes from the Protocol

Protocol section 13.6.6 mentions that the prior and concomitant medications will only be listed. Along with the listing, a summary table will also be provided.

7.0 Protocol Modifications

7.1 Modifications to the Approved Clinical Study Protocol

Protocol versions 2 and 3 are updated to align procedures across protocols in the program and provide clarification on the procedures.

Version 4.0 is updated to broaden the range of eligible participants by revising the participant eligibility criteria.

The primary purpose of version 5.0 is to add a Part B study to explore the safety and efficacy of longer duration dosing for 28 days instead of 14 days in Part A. Associated changes to the planned number of participants, planned study duration and duration of treatment, schedule of assessments, and sample size and power based on the Part B study have been incorporated.

7.2 Modifications to the Approved Statistical Analysis Plan

None.

7.3 Modifications to the Approved DMC Charter

Not applicable

8.0 Study Objectives

8.1 Primary Objective

- Evaluate the safety and tolerability of orally administered SAGE-718 in participants with Parkinson's disease mild cognitive impairment (PD-MCI).

[Redacted]

- [Redacted]
- [Redacted]
- [Redacted]
- [Redacted]
- [Redacted]

9.0 Study Endpoints

9.1 Primary Endpoint

- Incidence of treatment-emergent adverse events (TEAEs)

9.2 Secondary Endpoints

- Change from baseline in vital signs, clinical laboratory analytes, and electrocardiograms (ECGs).
- Responses on the Columbia–Suicide Severity Rating Scale (C-SSRS).

[Redacted text block containing multiple paragraphs and bulleted lists, all obscured by black boxes.]

[Redacted text block containing several paragraphs and bullet points]

10.0 Study Design

10.1 Overall Design

This study will enroll up to 33 (11 in Part A and 22 in Part B) participants. Part A participants complete 14 days of dosing and Part B participants complete 28 days of dosing in the study. A total of 30 participants are expected to complete dosing in the study. Additional participants may be dosed if the early discontinuation rate is >10%.

This is an open-label study evaluating the safety and tolerability of SAGE-718 and its effects on [Redacted] in participants with PD-MCI. Eligible participants with a confirmed diagnosis of idiopathic PD by 2015 Movement Disorder Society (MDS) criteria at Screening and who meet MDS Task Force Criteria for MCI in PD (excluding the requirement for UK PD Brain Bank diagnostic criteria) will receive a 3.0 mg dose of SAGE-718 daily for 14 days (Part A) or 28 days for (Part B) within 1 hour of 30g fat meal.

The study consists of a Screening Period, a Baseline Period, a Treatment Period, and a Follow-Up Period. The Screening Period begins with the informed consent process for prospective participants, including caregivers. Subsequent screening assessments will be performed between Day -21 and Day -8 to determine eligibility, including assessments of [Redacted].

The Baseline Period will occur from Day -7 through Day -1. During this period, each participant will receive dietary counseling to aid in choosing a morning meal containing approximately 30 g of fat for dosing. On Day -7 (± 1 day), participants will visit the clinic for confirmation of continued eligibility and collection of baseline [Redacted] and safety data.

The Treatment Period will begin on Day 1 and continue through Day 14 in Part A and Day 28 in Part B. During this time, participants will self-administer 3.0 mg SAGE-718 (as six 0.5-mg oral tablets), once per

day in the morning within 1 hour after initiating a meal containing approximately 30 g of fat. Participants will continue to complete daily assessments of [REDACTED] via a mobile device either remotely (at home), or in the clinic at scheduled visits and will track IP dosing and pre-dose food intake in a participant diary. Participants will complete daily remote assessments of [REDACTED]. For Part A the treatment period clinic visits will occur on Day 1, Day 7 (± 1 day), and Day 14, and for Part B it will be on Day 1, Day 7 (± 1 day), Day 14 (± 1 day), Day 21 (± 1 day) and Day 28. Following pre-dose procedures, participants will eat a morning meal and take the IP under staff supervision within 1 hour after initiating the meal. At scheduled clinic visits during the treatment period, safety, efficacy, and [REDACTED] will be performed, and study staff will dispense a sufficient amount of SAGE-718 for daily administration until the next scheduled study visit. In addition to weekly clinic visits, study staff will contact participants by telephone on Day 4 in both Part A and Part B to document any TEAEs and/or changes in concomitant medications

The Follow-Up Period. study staff will contact participants by telephone on Day 21 (± 1 day) for Part A to document any AEs and/or changes in concomitant medications. Participants will then return to the clinic on Day 28 (± 2 days) for a follow-up visit. In Part B, participants will return to the clinic for follow-up visits on Day 35 (± 1 day) and Day 42 (± 2 days). No formal interim analysis or DSMB review is planned for this study.

10.2 Sample Size Considerations

No formal sample size calculation was made for this study. Up to 10 participants completing 14 days of dosing in Part A and 20 participants completing 28 days of dosing in Part B are considered sufficient to assess preliminary safety and tolerability and for signal-finding of [REDACTED] after repeated daily dosing with SAGE-718. Assuming a 10% dropout rate, approximately 33 total participants will be required to obtain 30 completers. Additional participants may be dosed if the early discontinuation rate is $>10\%$.

10.3 Randomization

This study does not involve any randomization of participants.

11.0 Analysis Sets

11.1 Safety Set

The Safety Set will include all participants who were administered at least one dose of an investigational product (IP). Safety set will be used to describe the safety data.

11.2 Full Analysis Set

The Full Analysis Set will include all participants in the Safety Set with baseline and at least one postbaseline efficacy evaluation.

[REDACTED]

[REDACTED]

12.0 Interim Analyses

There are no planned interim analyses for this study.

13.0 Statistical Methods

13.1 General Statistical Methodology

All analyses will use SAS version 9.4 or higher.

Unless otherwise noted, continuous variables will be summarized using the number of observations (n), mean, standard deviation (std), median, first quartile (Q1), third quartile (Q3), minimum, and maximum values. The minimum and maximum values will be displayed to the same level of precision as the raw data; the mean, median, Q1, and Q3 values to one additional decimal place and the std to two additional decimal places.

Categorical variables will be summarized using counts and percentages. Percentages will be rounded to one decimal place, except 100% will be displayed without any decimal places, and percentages will not be displayed for zero counts.

Any data points that are not within the expected range due to subjects not following task instructions to complete the tasks will be flagged as invalid by CANTAB EDC. These data points will be excluded from the analyses and reports.

All participants will be used in the analyses as per the analysis populations, using all non-missing data available. No imputation process will be used to estimate missing data.

For all safety, efficacy, and other analyses, where applicable, the baseline is defined as the last assessment prior to the first dose of study IP.

All summary tables will be reported separately for Part A and Part B studies.

For [REDACTED], the baseline is defined as the average assessments over 7 days immediately preceding Day 1.

Prior and concomitant medication start/stop date imputation and adverse event start/stop date imputation are described in Appendix 2 and Appendix 3, respectively.

AEs will be coded using Medical Dictionary for Regulatory Activities (MedDRA) version 23.0u. All TEAEs are defined as an AE with onset after the first dose of IP or any worsening of a preexisting medical condition/AE with onset after the start of IP and throughout the study.

13.2 Participant Analysis Sets

The number and percentage of participants in the FAS, Safety, and [REDACTED] will be provided.

13.3 Participant Disposition

The number and percentage of participants screened, screen failed, enrolled in the study will be presented, together with the number and percentage of participants who discontinued from the study prematurely and a breakdown of the corresponding reasons for discontinuation as well as the number and percentage of participants who discontinued early from treatment and corresponding reasons.

Participant disposition will be summarized overall for the Safety analysis set, including the following:

- Number and percent of participants who completed the study (or treatment)
- Number and percent of participants who did not complete the study (or treatment) and reasons for early discontinuation of study (or treatment)

The denominator of the percentages will be based on the Safety analysis set. A by-participant disposition listing will be provided. In addition, a separate listing of screening failures with the primary reason for screen failures will be provided.

13.4 Eligibility Criteria Violations and Protocol Deviations

Protocol deviations identified during the study will be captured and categorized by the study team review as major and minor deviations on an ongoing basis. In addition, COVID-19 related protocol deviations such as remote telephone/video visit/assessment, home healthcare visit, missed visit/assessment, out of window visit/assessment, safety reporting, investigational product administration, and others will be documented and analyzed as appropriate.

All major protocol deviations will be summarized by using the FAS.

A by-participant listing of all protocol deviations will be provided with columns identifying the following: date of the deviation, type of deviation (Major/Minor), deviation category, and verbatim description.

13.5 Demographic and Baseline Characteristics

Demographic and baseline characteristics, such as sex, race, age, height (cm), baseline weight (kg), body mass index (BMI) (kg/m²), years since the first diagnosis of Parkinson's disease, and Hoehn and Yahr stage will be summarized using the Safety analysis set. Data will be summarized using descriptive statistics including sample size (n), mean, std, median, Q1, Q3, minimum, and maximum for continuous variables and numbers and percentages of participants for categorical variables.

The baseline for weight, height and BMI is defined as the last non-missing value prior to the first dose of the investigational product.

13.6 Medical and Surgical History

Medical/surgical procedure history collected at screening will be coded using the Medical Dictionary for Regulatory Activities (MedDRA), Version 23.0u. Medical/surgical procedures history data will be summarized by system organ class (SOC) and preferred term (PT) using the Safety analysis set. A summary of medical/surgical history that is ongoing at the time of screening will be provided separately. Medical/surgical procedures history will also be listed.

13.7 Physical/Neurological Examinations

The physical examination will be conducted at Screening (Day -21 to Day -8) and baseline (Day -7 and Day -1), as well as the end of the scheduled dose day or ET.

A full physical examination will occur at Screening and will include an assessment of body systems (eg, head, eye, ear, nose and throat; heart; lungs; abdomen; and extremities) as well as neurological examination. Thereafter abbreviated physical examinations will include an assessment of general appearance, cardiovascular, respiratory, gastrointestinal, and neurological systems, followed by a targeted physical examination as needed.

Clinically significant abnormalities found during Screening or clinic visits will be reported on the medical history CRF; clinically significant abnormalities or worsening conditions will be reported on the adverse event CRF, hence will be captured in AE displays. Therefore, no summaries will be done for physical and neurological examinations.

13.8 Prior and Concomitant Medications

The following analyses will use the Safety Set.

All medications taken and procedures undergone during the study will be recorded.

Medications will be presented according to whether they are being taken prior to and/or during the study (concomitant). Prior medications are defined as those taken prior to the initiation of the start of the investigational product, and that ended prior to the IP. Concomitant medications are defined as those with a start date on or after the first dose of investigational product or those with a start date before the first dose of investigational product that is ongoing or with a stop date on or after the first dose of investigational product.

13.9 Treatments

13.9.1 Extent of Investigational Product Exposure and Treatment Adherence

The following analyses will use the Safety Set.

Total drug exposure (in mg) is defined as the total investigational product in mg for SAGE-718 that was taken during the study.

Total exposure duration to investigational product (in days) is defined as the date of last dose – date of first dose + 1. Note that this does not exclude days when the dose has been missed

The percentage of the planned exposure received is defined as the total drug exposure, divided by planned exposure, times 100. For participants who complete the treatment period, planned drug exposure is the number of days of treatment planned times 3 mg. For participants who discontinued the treatment early, the planned drug exposure is the number of days (last dose date – first dose date + 1), times 3 mg.

Investigational product adherence (%) is defined as the number of tablets taken, divided by the number of tablets planned to be taken, times 100. The schedule of investigational product is six tablets per day.

The number of tablets planned to be taken is defined as follows:

- If the participant discontinues treatment within Day 2 and Day 14 (both inclusive), the number of tablets planned to be taken is the last dose day of investigational product × 6.
- If the Part A participant does not discontinue treatment, the number of tablets planned to be taken is 84 (6x14) whereas for Part B it is 168(6x28).

Investigational product exposure and adherence will be summarized descriptively and listed. The number and percentage of participants with investigational product adherence in categories(<80%, 80-100%, >100%) will be provided. Investigational product accountability will be listed.

All investigational product exposure data will be in by-participant listings, as well as a summary of treatment adherence.

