7.4. Dose Adjustment Criteria

Dosing may be interrupted in an individual participant due to an AE considered by the investigator to be related to IP, however, no individual dose reductions will be permitted.

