11.2.1.1. Blood Sample Collection

Plasma samples for [REDACTED] will be collected according to the sampling collection times specified in Table 2, [REDACTED] Table 4, and [REDACTED]. The start day of IP administration is Day 1, and all postdose sampling times are relative to this time.

An additional [REDACTED] may be collected at any time if clinically indicated and at the discretion of the investigator (eg, for unusual or severe AEs).

Each sample will be marked with unique identifiers with at least the study number, participant number, and the nominal sample time. The date and actual time that the blood sample was taken will be recorded on the case report form. Samples will be shipped according to the instructions in the laboratory manual.

[REDACTED]
[REDACTED]

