13.6.1. Adverse Events

AEs will be coded using Medical Dictionary for Regulatory Activities version 22.0 or higher. A TEAE is defined as an AE with onset after the first dose of IP. The analysis of AEs will be based on the concept of TEAEs. The incidence of TEAEs will be summarized by System Organ Class and preferred term. In addition, summaries will be provided by intensity (mild, moderate, severe) and by causality (related, not related) to IP.

Any TEAEs leading to discontinuation or interruption of treatment or withdrawal from the study and any treatment-emergent SAEs will be summarized.

All AEs and SAEs (including those with onset or worsening before the start of IP) through the end of the study will be listed.

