19.7 Appendix-G Tables, Figures, and Listings

Table Number	Title	Population
Table 14.1.1.1A	Subject Analysis Sets - Part A	All Screened Subjects
Table 14.1.1.1B	Subject Analysis Sets - Part B	All Screened Subjects
Table 14.1.1.2A	Subject Disposition - Part A	Safety Analysis Set
Table 14.1.1.2B	Subject Disposition - Part B	Safety Analysis Set
Table 14.1.1.3A	Major Protocol Deviations - Part A	Full Analysis Set
Table 14.1.1.3B	Major Protocol Deviations - Part B	Full Analysis Set
Table 14.1.2.1A	Demographic Characteristics - Part A	Safety Analysis Set
Table 14.1.2.1B	Demographic Characteristics - Part B	Safety Analysis Set
Table 14.1.3A	Prior Medications by ATC Classification and WHO Drug Dictionary Preferred Term - Part A	Safety Analysis Set
Table 14.1.3B	Prior Medications by ATC Classification and WHO Drug Dictionary Preferred Term - Part B	Safety Analysis Set
Table 14.1.4A	Concomitant Medications by ATC Classification and WHO Drug Dictionary Preferred Term - Part A	Safety Analysis Set
Table 14.1.4B	Concomitant Medications by ATC Classification and WHO Drug Dictionary Preferred Term - Part B	Safety Analysis Set
Table 14.1.5A	Medical and Procedures by System Organ Class and Preferred Term - Part A	Safety Analysis Set
Table 14.1.5B	Medical and Procedures by System Organ Class and Preferred Term - Part B	Safety Analysis Set
Table 14.1.6A	Medical and Procedures that are Ongoing at the time of Screening by WHO Drug Dictionary Preferred Term - Part A	Safety Analysis Set
Table 14.1.6B	Medical and Procedures that are Ongoing at the time of Screening by WHO Drug Dictionary Preferred Term - Part B	Safety Analysis Set
Table 14.1.7A	Summary of Exposure and Adherence - Part A	Safety Analysis Set
Table 14.1.7B	Summary of Exposure and Adherence - Part B	Safety Analysis Set

[figure not shown]

[figure not shown]
Table 14.3.1.1A	Overall Summary of Treatment Emergent Adverse Events - Part A	Safety Analysis Set
Table 14.3.1.1B	Overall Summary of Treatment Emergent Adverse Events - Part B	Safety Analysis Set
Table 14.3.1.2A	Treatment-Emergent Adverse Events by System Organ Class and Preferred Term - Part A	Safety Analysis Set

Table 14.3.1.2B	Treatment-Emergent Adverse Events by System Organ Class and Preferred Term - Part B	Safety Analysis Set
Table 14.3.1.3A	Treatment Emergent Adverse Events Leading to Discontinuation of the Study by System Organ Class and Preferred Term - Part A	Safety Analysis Set

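### The SAP specifies no summary of TEAEs leading to dose interruption, although the protocol promises one, and its planned-exposure percentage does not register early stopping

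*SAP*

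**What the plan says.** **Interruption.** Protocol 7.4 lets dosing be interrupted for an AE that the investigator considers related to IP, and adds that "no individual dose reductions will be permitted". Protocol 12.2.1 makes interruption one of the conditions that turn a laboratory, vital-sign or ECG change into a reportable AE. Protocol 12.2.4 has action taken recorded for each AE. Protocol 13.6.1 then commits to summarizing "Any TEAEs leading to discontinuation or interruption of treatment or withdrawal from the study", together with treatment-emergent SAEs.

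SAP 16.1 defines one action-taken flag, Drug Withdrawn, for AEs leading to treatment discontinuation. SAP 6.1 declares one departure from the protocol, an added medication table.

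**Exposure and adherence.** SAP 13.9.1 divides total mg taken by planned mg. For completers, planned mg is the planned number of days times 3 mg. Otherwise: "For participants who discontinued the treatment early, the planned drug exposure is the number of days" from first to last dose inclusive, times 3 mg.

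Tablet adherence is tablets taken over tablets planned. "The schedule of investigational product is six tablets per day", with 84 tablets planned for Part A and 168 for Part B when treatment is not discontinued. The rule for discontinuers reads "If the participant discontinues treatment within Day 2 and Day 14 (both inclusive"), in which case "the number of tablets planned to be taken is the last dose day of investigational product" times 6. Both measures are reported in Table 14.1.7A, "Summary of Exposure and Adherence - Part A", and its Part B counterpart, Table 14.1.7B.

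**The concern.** The study's primary objective is safety and tolerability. Because individual dose reductions are not permitted, interruption is the only AE-driven change to an individual's dosing short of stopping. A reader of the protocol expects to find it tabulated. A reader of the SAP finds no definition, no row and no statement that it was dropped.

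The exposure percentage has a labelling problem. Its name suggests the share of the assigned course that was received. For someone who stops early, numerator and denominator shrink together, so the figure measures how completely doses were taken up to the last one. Tablet adherence already measures that, so the SAP has no percentage that shows how much of the course was delivered.

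At stake is the accuracy of supporting tolerability reporting. TEAE incidence, the primary endpoint, does not depend on either point.

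**Working it through.** **1. Protocol 13.6.1 against the SAP table list (19.7)**

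| Promised summary | SAP table |
|---|---|
| TEAEs leading to treatment discontinuation | 14.3.1.6A/B |
| TEAEs leading to study withdrawal | 14.3.1.3A/B |
| Treatment-emergent SAEs | 14.3.1.4A/B |
| TEAEs leading to interruption | none |

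The other AE tables cover the overall summary (14.3.1.1), class and term (14.3.1.2), death (14.3.1.5), relationship (14.3.1.7) and severity (14.3.1.8). The items that SAP 16.1 names for the overall summary are event count, any TEAE, related TEAE, maximum severity, discontinuation, SAE and death. Interruption is not among them. Numbering from 14.3.1.1 to 14.3.1.8 has no gap, and neither SAP 16.1 nor that stretch of the list shows a redaction. For scale, one participant with an interruption would be 1/11 = 9.1% of Part A or 1/22 = 4.5% of Part B. The actual number is unknown.

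**2. Planned-exposure percentage**

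Inputs: six 0.5 mg tablets = 3.0 mg daily (Protocol 10.5); course length D = 14 or 28 days (Protocol 7.3); "The start day of IP administration is Day 1" (Protocol 11.2.1.1).

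The plan's own figures reproduce: 6 × 14 = 84 and 6 × 28 = 168 tablets, which are 84 × 0.5 = 42 mg and 168 × 0.5 = 84 mg.

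For a discontinuer with last dose day d and m missed days before it:
- SAP percentage = 3(d − m) / 3d
- tablet adherence = 6(d − m) / 6d, the same value; in general, for T tablets, 0.5T / 3d = T / 6d
- share of the assigned course = 3(d − m) / 3D

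| Case | SAP % | Tablet % | Share of course |
|---|---|---|---|
| Part A, last dose Day 3, none missed | 9/9 = 100 | 18/18 = 100 | 9/42 = 21.4 |
| Part B, last dose Day 3, none missed | 9/9 = 100 | 18/18 = 100 | 9/84 = 10.7 |
| Part A, last dose Day 3, one missed | 6/9 = 66.7 | 12/18 = 66.7 | 6/42 = 14.3 |
| Part B, last dose Day 3, one missed | 6/9 = 66.7 | 12/18 = 66.7 | 6/84 = 7.1 |
| Part B, last dose Day 20, two missed | 54/60 = 90.0 | no rule | 54/84 = 64.3 |
| Part B completer, seven missed | 63/84 = 75.0 | 126/168 = 75.0 | 63/84 = 75.0 |

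Missed doses lower the SAP percentage; stopping does not.

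Effect on the mean at the planned 10% dropout (0.10 × 22 = 2.2, taken as 2; 0.10 × 11 = 1.1, taken as 1), with no missed doses. The SAP mean is 100% throughout. The full-course means are:
- Part B, 2 of 22 stop. Day 3: (2000 + 2 × 10.71)/22 = 91.9%. Day 14: (2000 + 2 × 50)/22 = 95.5%. Day 21: (2000 + 2 × 75)/22 = 97.7%. Day 27: (2000 + 2 × 96.43)/22 = 99.7%.
- Part A, 1 of 11 stops. Day 3: (1000 + 21.43)/11 = 92.9%. Day 7: (1000 + 50)/11 = 95.5%. Day 13: (1000 + 92.86)/11 = 99.4%.

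**Two denominators for one person.** Protocol 8.4.1 invites participants who stop IP to attend visits through the end of the Treatment Period. Someone in Part B last dosed on Day 3 who does so could be classed as an early discontinuer (9/9 = 100%) or as having completed the period (9/84 = 10.7%). The SAP does not say which.

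**3. Tablet rule**

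The SAP does not say whether the day of discontinuation is the last dose day or the first day without a dose. If the former, Part B last-dose Days 1 and 15–27 have no rule; if the latter, Days 14–27 have none. Days 15–27 are uncovered either way. At the planned dropout this concerns about 0 to 2 people.

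**The case against.** The best defence is that little is hidden. SAP 13.9.1 states its denominator openly, and no hypothesis test uses the percentage. Four points stand and set the limits of this finding.

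- A reader might infer that early stopping disappears from the report. It does not: total mg, exposure duration, disposition with reasons (SAP 13.3) and Tables 14.3.1.6A/B all show it.
- A reader might infer that interruptions leave no trace in the tables. Doses missed before the last one lower both percentages and can move a participant into the under-80% adherence category. What is missing is their attribution to an AE.
- A reader might infer that the SAP cancels the protocol's commitment. SAP 6.0 says that it is to be read with the protocol, and the listed contents of the overall TEAE summary need not be exhaustive. The supportable statement is that the SAP does not specify the summary.
- A reader might infer that the two percentages are always identical. For early stoppers that requires mg and tablets to come from the same count and the participant to be classed as discontinued. Protocol 9.4 draws on diary, packaging and returned tablets, and the SAP lists administration, accountability and adherence separately (Listings 16.2.5.1 to 16.2.5.3). The Protocol 8.4.1 case also breaks the equality if the full-course denominator is applied.

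The defence does not answer why one of four promised summaries has no table, or why a percentage labelled as planned exposure leaves out the undelivered part of the plan.

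**Conclusion.** The point holds, at low severity. The SAP does not specify the promised summary of TEAEs leading to interruption and does not declare the omission, so AE-attributed interruptions would be identifiable only in listings. The planned-exposure percentage does not fall when a participant stops early. At the planned dropout it overstates the mean share of the course by 0.3 to 8.1 points in Part B and 0.6 to 7.1 points in Part A; the upper ends require every dropout to stop by about Day 3. The tablet rule has a small gap for Part B last-dose Days 15–27.

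The figures assume 3.0 mg daily throughout (Protocol 7.4.2 allows the dose to be reconsidered for later participants), no missed doses in the mean scenarios, and dropout as planned. The effect is confined to supporting tolerability reporting.

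**What to change.** 1. In SAP 16.1, define a TEAE leading to interruption from the action-taken field, and add a row with number and percentage of participants to Tables 14.3.1.1A and 14.3.1.1B. If the summary is not wanted, declare that in SAP 6.1.
2. In SAP 13.9.1, compute the planned-exposure percentage against the full assigned course for every participant, whatever the completion status: 42 mg in Part A and 84 mg in Part B at 3.0 mg daily. This also settles the Protocol 8.4.1 ambiguity. Keep tablet adherence as the single on-treatment measure, with no second mg version. The two will still agree for completers, as they should, and will differ for early stoppers.
3. Apply last dose day × 6 to any early discontinuation in either Part.

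The cost is a few lines of SAP text, one changed denominator and one row per Part. No new data are needed if the action-taken codes separate interruption from withdrawal; the CRF is not among the documents, so this needs checking. If anyone stops early, the reported mean exposure percentage will be somewhat less favourable.
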